**Hiring and Training Outcome Assessors and Intervention Facilitators.** Our research team will initially come from our existing team who worked on the previous study and/or who have previously conduct adolescent focused HIV/STI prevention research and interventions. Then we hire additional team members if needed based on experience relevant to the study. Our team will be split into an outcome assessment team (based at DTHF) for Aim 1 and an intervention team (based at Department of Psychiatry at UCT). We will draw from both for Aim 3. Our investigative team will train our outcome assessment team in data systems, procedures, protocols, and forms using mock training as well as in-field practice to ensure quality data collection and preparation for successful tracking and tracing. Outcome assessors will be *blinded*. We will also train our intervention and fidelity team in protocols, procedures, and forms including randomization and delivery of the *Our Family Our Future* intervention. Training will involve 4 modules. Module 1 includes: 1) introductions and ice-breaking exercises, 2) project overview and training objectives, 3) education regarding depression, HIV, parenting, family communication, gender roles and social norms particularly in regards to sexual relationships, and sexual relationship negotiations. Module 2 focuses on intervention facilitation skills: 1) public speaking and 2) communication of sensitive topics. Module 3 involves training in use of the manualized intervention protocol including: 1) demonstrations of intervention modules, 2) education on core intervention elements, and 3) role-play. Module 4 involves: 1) testing facilitation skills in short mock scenarios, 2) feedback from the PIs. We incorporate challenges that may arise during intervention implementation including delivery of intervention content and inter-personal interactions to assess facilitators' mastery of core. We rank performance using fidelity forms. If an interventionist is not deemed qualified, additional training will be provided until competent. Interventionists deemed unqualified will be replaced.

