## 2. Study design

**Summary of scientific design.** We test the efficacy of *Our Family Our Future* in a 2-arm, single blinded RCT with 6- and 12-month follow-ups. Participants include a sample of N=880 adolescents 14-16 years (and 880 parents) who will be randomized based on permuted blocked randomization (balancing by gender) to an intervention arm (n=440 adolescents and their parents testing *Our Family Our Future*) or a control arm (n=440 adolescents and their parents) of usual care. Study design carefully adheres to elements outlined in the Consolidated Standards of Reporting Trials (CONSORT) Statement. This pilot study adheres to a single blind, randomized pilot trial design with the end goal of informing a full-powered RCT corresponding to a Phase III

---

 The 12-month follow-up with parents and teens may occur up to 24 months afterwards in order to retain as many teen/parent dyads as possible in the longitudinal analysis.

clinical trial. Outcomes will be assessed at baseline, 6 months, and 12 months after the last intervention session. Due to the COVID-19 crisis (March, 2020) we will attempt to first abide by the scheduled 6- and 12-month outcome timepoints for all self-reported and behavioral data with biological data (HIV and STIs) captured when movement restrictions are lifted and/or when physical contact is acceptably safe. If this does not work, we will shift to collecting all 6- and 12-month timepoints for all data to when movement restrictions are lifted and/or physical contact is acceptably safe. The count-down clock for the 6 months and 12 months outcome evaluations will occur after the last intervention session has occurred. Feasibility data and process data on possible mechanisms of change will be collected at eligibility, enrollment, during the intervention sessions, and during baseline and follow-up assessments.

**Study questions.** The primary study questions are:

Question 1: Is this intervention efficacious? That is, is there evidence of hypothesized effects of the intervention, that the intervention will reduce or maintain symptoms that fall below the clinically significant range for depression and reduce or delay actual or intended sexual risk behavior in adolescents?

Question 2: What mediates and moderates the effect of the intervention on the main outcomes?

Question 3: What are the barriers and facilitators of intervention implementation?

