policy relevance, and strike a balance between costs while protecting the integrity of our main scientific goal, to have enough power to thoroughly examine the main outcomes.

**Sample Size and Power Considerations.** We use data from our preliminary pilot study and other relevant secondary sources to formulate a realistic range of necessary assumptions for sample size and power considerations for primary outcomes. As shown in Table 1 we estimate that a total sample size of 880 adolescents, or 440 adolescents per arm, will be required to adequately power our study.

[figure not shown]

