**Eligibility Assessment, Enrollment, and Randomization.** The study staff will assess *eligibility*. Eligibility for parents and eligibility for adolescents will be individually determined. Eligibility will be auto-calculated using a pre-programmed computerized method using our secure mobile project-dedicated android phones or “survey devices” that are part of our field-based data collection system (see details on SurveyToGo software used for data collection). The survey devices will automatically calculate eligibility based on the inclusion/exclusion criteria outlined above. Final eligibility will be determined by dyadic eligibility (that is both parents and adolescents have to be eligible to be invited to participate in this family-based intervention). Eligible parent-adolescent dyads will be invited to participate in the baseline assessment and attend an enrollment session where randomization will occur. If interested, each individual in the dyad will be go through individualized informed consent and assent processes. After completing baseline data collection, each individual in the dyad will be issued matching “invitation tickets” to attend the enrollment session. Invitation tickets provide participants with date and location of the enrollment session. These invitation tickets also display unique ID numbers to allow us to verify at the enrollment session that we have screened individuals for eligibility (by matching unique ID numbers on the ticket with our data system) and help us ensure scheduling of dyads. Dyads will attend an enrollment session where trained study staff will answer questions about the study. Following this information session, study staff will gather voluntary informed consent and assent forms from interested individuals. If consent and assent are obtained for a complete dyad, trained study staff will use a computerized block randomization procedure using our FileMaker Software which automatically determines dyad assignment to the intervention or control group based on programming out [name] and our data team. The block randomization procedure will balance allocation dyads for adolescent gender. Dyads assigned to the intervention group will receive the first intervention session that same day. Dyads assigned to the control group will be given usual care (consisting of a packet of existing available brochures on HIV, STIs, mental health including places to access care). Because randomization occurs in a group setting, assignment is not concealed from participants or from study staff who are part of the intervention team or fidelity

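### The plan does not protect upcoming allocations from prediction: open group randomisation in gender-balanced permuted blocks, with no rule that all consents come first

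*Combined protocol and SAP*

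**What the plan says.** Section 2 (Study design) specifies permuted blocks with balance on gender, for "a total sample size of 880 adolescents, or 440 adolescents per arm". Section 3, under Eligibility Assessment, Enrollment, and Randomization, repeats the stratifying factor: "The block randomization procedure will balance allocation dyads for adolescent gender".

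The same part of Section 3 gives the sequence. Dyads come to an enrolment session, hear about the study, and hand in consent and assent forms. Then: "If consent and assent are obtained for a complete dyad, trained study staff will use a computerized block randomization procedure using our FileMaker Software". Intervention dyads start their first session that day and control dyads receive a packet of brochures. On openness it says: "Because randomization occurs in a group setting, assignment is not concealed from participants or from study staff who are part of the intervention team". The fidelity team is included; only the outcome assessors are kept unaware.

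Section E (Consent and Assent Procedures) shows that this is a second, real decision point. Consent is sought again after a staff-led discussion for and against taking part, and dyads may still decline.

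On who operates the system, Section 3 says only that trained study staff do. The paragraph on hiring and training assessors and facilitators says the investigators will "train our intervention and fidelity team in protocols, procedures, and forms including randomization and delivery" of the programme. Section F (Data Privacy and Protections) describes FileMaker as the randomisation and tracking database and restricts it to staff who track participants. The hiring paragraph prepares the assessment team for that tracking.

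**The concern.** Computer generation stops anyone looking up an assignment before that dyad has consented. It does not stop inference from assignments already seen. Within a permuted block the arms must even out, so someone who sees past assignments and the adolescent's gender can tell which arm is behind and, near the end of a block, which arm must come next.

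If this happens while other dyads at the session are still deciding, the order in which dyads are entered, or the encouragement given to a hesitant dyad, could depend on the expected arm. That would be selection bias at entry. It could affect any outcome. The baseline comparison and covariate adjustment planned in Section 6 would only partly repair it, because they reach measured variables alone.

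**Working it through.** The plan states no figure for predictability, so there is none to reproduce.

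**Inputs from the documents.** 880 dyads, 1:1, permuted blocks, balance on gender (Sections 2 and 3); assignments visible to participants and to the intervention and fidelity teams (Section 3).

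**Assumptions, because the documents are silent.** Block size 2 to 8; separate blocks for girls and boys, 440 dyads each; 10 or 20 dyads per session for the batched case.

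**Formulas for a fixed block of size 2m with all earlier assignments seen**

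- Share of allocations certain in advance (one arm already used up in the block) = 1/(m + 1). This needs a known, fixed block size.
- Best-guess hit rate (Blackwell-Hodges convergence strategy: name the arm that is behind, toss a coin if level) = [m + (4^m / C(2m, m) − 1)/2] / (2m). This guess needs the tally by gender but not the block size.

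Worked for blocks of 4 (m = 2): the certain share is 1/3, and 880/3 = 293 dyads. The hit rate is [2 + (16/6 − 1)/2]/4 = 2.833/4 = 0.708.

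For the batched case, two gender strata were simulated with the same guessing rule, but the tally was updated only after each session ended.

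| Block size | Certain share | Of 880 | Hit rate, dyad by dyad | Hit rate, batched, 10 per session | Hit rate, batched, 20 per session |
|---|---|---|---|---|---|
| 2 | 50% | 440 | 75.0% | 54.9% | 52.5% |
| 4 | 33% | 293 | 70.8% | 56.5% | 53.3% |
| 6 | 25% | 220 | 68.3% | 57.7% | 53.9% |
| 8 | 20% | 176 | 66.6% | 58.2% | 54.6% |

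Chance is 50%. As a check, the dyad-by-dyad case was also simulated and gave 74.9%, 70.9%, 68.4% and 66.7%, in line with the formula.

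**Varying the block size alone.** With dyad-by-dyad release and sizes drawn at random, the simulated hit rate is 69.2% (sizes 4 and 6), 70.3% (2, 4 and 6) and 68.1% (4, 6 and 8). Nearly all the gain therefore comes from completing consents first.

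**The case against.** The quoted sentence on openness concerns assignments already made. Its counterpart is the blinding of outcome assessors, and the Blinding paragraph in Section 2 treats it the same way. A reader might infer from it that staff can predict the next arm while consent is being taken. The documents do not say so.

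Three further inferences are tempting and also go beyond the text:

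- **That release is dyad by dyad.** The condition that a dyad's consent be complete can be read as an entry requirement rather than a statement of timing. For a group programme starting the same day, collecting all forms first is a natural reading. Nothing describes undecided dyads watching others being sent to the programme or handed brochures.
- **That the delivering team runs the randomisation.** Being trained in it makes this plausible, and keeping assessors unaware of assignment makes them unlikely operators. But Section 3 does not say it, and the FileMaker restriction in Section F fits it poorly.
- **That half of all allocations are known.** The figure of 440 needs blocks of 2, which nothing suggests, as well as a known block size and dyad-by-dyad release. The data team has a part in the programming, so session staff need not know the size.

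Existing safeguards also count. Recruitment approaches everyone, the survey device calculates eligibility, baseline data and first consent precede the session, and Section E steers staff away from persuasion. The documents give no evidence that bias would in fact occur.

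All of this stands, and it narrows the point. It does not remove it: the text allows the exposed procedure, says nothing to exclude it, and leaves a consent decision open at the session where assignments become visible.

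**Conclusion.** The point holds as a gap in protection, not as demonstrated predictability. The plan combines permuted blocks, a visible balancing factor, open assignments and a trigger tied to each dyad's consent, and states no safeguard for upcoming allocations beyond software that assigns after consent.

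The size depends on what the plan leaves out. Under dyad-by-dyad release with a tally by gender, the best guess is right 67-75% of the time, and 20-50% of allocations are certain if a fixed block size of 2 to 8 is also known. Under batched consent the hit rate is about 52-58%, close to chance, given the assumed session sizes. The exposure covers only the second consent and the order of entry. If the sponsor already batches consents, saying so, along with who randomises and who knows the block sizes, would largely settle the matter.

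**What to change.** In Section 3, under Eligibility Assessment, Enrollment, and Randomization:

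1. Complete the second consent and assent for all dyads at the session, then lock the list of consented dyads in FileMaker.
2. Only then release all allocations for that session in one batch, in the locked order, with no additions or reordering. Latecomers go to the next session.
3. As a supplement, draw block sizes at random within gender and withhold them from session staff. This removes certainty about the next arm, but alone it leaves the hit rate at 68-70%, so it cannot replace steps 1 and 2.
4. State who operates the randomisation, and reconcile Section 3 with the hiring and training paragraph and with the FileMaker access rule in Section F.

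The cost is a paragraph of protocol text, a change to the FileMaker script and a short wait for dyads at each session. Balance on gender is kept.

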#### **4. Research Procedures and Data Collection Methods**

All study procedures will be conducted in the language preferred by participants (isiXhosa or English) and all materials will be offered in the language of preference by participants.

**Aim 1 - Intervention Procedures.** *Our Family Our Future* is a 'selective' behavioral prevention program, designed to address HIV/STI acquisition, sexual risk behavior, and depression among adolescents (ages 14-16) in communities with high HIV prevalence and from families where adolescents exhibit mild, potentially troublesome, depressive symptoms but do not reach the threshold for further screening for a significant clinical depressive disorder (we will recruit adolescents and parents with Center for Epidemiologic Studies Depression Scale scores of 9 to 15, which is a reliable, validated instrument for use in South Africa.) This intervention involves parent-child dyads who receive the intervention in a community setting, in a facilitated group format. Due to the COVID-19 crisis, we will also use, if necessary, a facilitated intervention delivered to individual families by phone. The intervention is comprised of 3-hour sessions, held weekly for 3 consecutive weeks with an individual family meeting in the third or fourth week depending on family desires. The intervention also includes take-home activities to deepen behavioral engagement with the week's received session and to "prime the pump" for the upcoming week's session. The final intervention covers the following topics in combined adolescent-parent sessions using role play, group activities, discussion and debate, and facilitation. In some modules parents and adolescents will have content delivered together and in some modules parents and adolescents will break out to parent-only or adolescent-only groups (the paired facilitators will split apart for these break out groups). The module cover the following for combined adolescent-parent sessions: 1) family needs and values; 2) community strengths and challenges; 3) communication skills; 4) talking about sensitive topics – HIV, STIs, sex, puberty, mental health, and discipline; 5) HIV and STI transmission, prevention, and living with HIV; 6) healthy individual and family coping with mental distress, adolescent sexual health, and other challenges; and 7) family goals and strategies for healthy interactions and problem-solving. There are also separate adolescent and parent sessions. For adolescents, topics include: 1) peer influences; 2) healthy relationships and gender roles and interpersonal violence; 3) sexual decision making and communication; 4) condom use and contraception; and 5) consequences of sexual decisions. For parents, these include: 1) adolescent development and reproductive health; 2) healthy relationships and gender roles; 3) psychoeducation including a focus on depression and child perspectives on depression; 4) communicating about sexual and mental health; and 5) condom use and contraception.

If the intervention is delivered in person, we offer refreshments for families at each intervention session. This intervention will be delivered at the Community Center owned by Desmond Tutu HIV Foundation. The intervention will be facilitated by an interventionist team, and observed by study staff (e.g., fidelity team, supervisor). We believe a trained interventionist team will be appropriate. The original depression preventive intervention (Family Talk) was designed for delivery by a wide range of health professionals. We will use non-specialist but trained intervention facilitators (hired from our pilot study where they were trained) or based on rigorous hiring of those who have previous experience as community health workers, home based care

volunteers, or health educators. We will provide intensive training, fidelity monitoring, and close supervision of non-specialist intervention facilitators to ensure ethical, professional, and quality delivery. We focus on a non-clinical setting because there is limited capacity to facilitate a preventive intervention in clinical care settings with 0.28 psychiatrists, 0.45 other medical doctors, 7.45 nurses, 0.32 psychologists, 0.4 social workers, and 0.28 other mental health workers per 100,000 population in South Africa. We purposefully build community capacity by training non-specialist intervention facilitators. This strategy is consistent with calls for task-shifting as a key strategy for addressing global mental health resource challenges; is cognizant of future scalability and sustainability; and minimizes strain the study might place on overburdened health systems. Task-shifting has been effective in mental health delivery in developing countries including depression interventions in South Africa Moreover, non-specialist intervention facilitators from the target community may increase acceptability. A study with vulnerable HIV-affected populations showed that non-specialist intervention facilitators were equally as effective as trained professionals, but participants were more satisfied with non-specialist intervention facilitators. Given the setting and context, and the preventive focus of this experimental intervention, this study will task-shift delivery to trained interventionists who have a background that would be contextually appropriate for a community-based intervention for HIV risk and depression and advances family prevention science in South Africa. Trained non-specialist intervention facilitators will deliver the intervention. To support fidelity, trained research staff will be present at all group intervention sessions to offer guidance and supervision to non-specialist intervention facilitators. We will also hold weekly team meetings to discuss the experience of intervention delivery, with the PI and Project Manager offering retraining if needed.

**Aim 3 - In-depth interview procedures.** Interviews will last 1 to 1.5 hours and take place in a private room at University of Cape Town or in the community intervention site. Due to the COVID-19 crisis, we will default to interviews by phone as needed. Sociodemographic and behavioral data will be gathered during Aim 1. We use a semi-structured agenda to guide qualitative interviews organized by exemplar key questions; exact wording will vary depending on language and cultural norms and will explore these themes: (1) barriers and facilitators to attendance and intervention participation, particularly in relation to scale-up and implementation; (2) acceptability of intervention strategy; (3) predicted behavioral impacts of intervention content including areas that need further refinement and strengthening; (4) advice on format, frequency, timing, and delivery aspects to facilitate future scale-up and dissemination; (5) organizational considerations including advice on gaining buy-in from key gatekeepers; (6) open solicitation of other key considerations for future dissemination, scale-up, and implementation. We record interviews using a digital voice recorder (DVR). At the close of each interview, we will thank participants and provide reimbursement.

**Assessment Procedures.** Well established measures with good reliability and validity were piloted in the preliminary studies.

Table 2: Outcome Measures and Assessment Timeline				
Outcome	Measures	Baseline	3-mth	12-mth
HIV Risk Behavior & Intentions: biologically verified HIV, STIs; prior and planned pregnancy and contraception; sex	• Items taken from South African trials & NIH's Adolescent Medicine Trials Network for HIV/AIDS Interventions; Sexual Experiences Survey 	✓	✓	✓

frequency; partner number; condom use; sex refusal				
Depression: depression symptom severity	• Center for Epidemiologic Studies Scale - Revised (CESD-R) adult and child versions 	✓	✓	✓
Co-variates: socio-demographics; economic status; household characteristics	• Items from the South African Census Questionnaire, World Health Organization Food Security Questionnaire;  Verbal Symptom and Autopsy Questionnaire for HIV illness and AIDS orphanhood 	✓	✓	✓
Mediators & Moderators:	
 
• South African HIV Knowledge; AIDS Related Stigma Scale and Internalized AIDS-Related Stigma Scale; Condom Attitudes Scale; Condom Use Self-Efficacy; Condom-use skills checklist
 
• Depression Impairment Scale for Parents, Children Perceptions Of Other's Depression Scale-Mother Version – shortened; Beck Anxiety Inventory and Hopelessness Scale; Children's Manifest Anxiety Scale Revised II; Strengths and Difficulties Questionnaire; National Stressful Events Survey Short Scale and PCL5 for PTSD; K6 for psychological distress
 
• Alabama Parenting Questionnaire-Short Form; Family Relationship Inventory; Family Problem Solving Communication; Parent-Adolescent Sex Communication; Inventory of Parent and Peer Attachment; Parental Monitoring Questionnaire; Alcohol Use Disorders Identification Test, Drug Use Disorders Identification Test
 
• Connor-Davidson Resilience Scale; Multi-dimensional Scale of Perceived Social Support
 
	✓	✓	✓
COVID-19 Measures	We use an adapted version of the CRISIS tool from the US National Institute of Mental Health to capture COVID-19 impact ( https://github.com/nimh-mbdu/CRISIS )			

We investigate efficacy regarding whether the intervention, relative to the control, will produce: (1) reduced incidence of HIV/STIs; (2) reductions in actual or intended HIV/STI risk behaviors; (3) reductions in depressive symptoms at baseline, 6- and 12-months. For adolescents at each visit, we will capture biologically verified HIV/STIs through HIV tests (dried blood spot) and urine tests for Chlamydia trachomatis and Neisseria gonorrhoeae (Xpert CT/NG assays) (see details on collection, sensitivity, and specificity in Appendices: HIV/STI Test); STIs were chosen based on prevalence in the target population. All new positive HIV/STI cases will be referred for treatment at the DTHF youth center clinic or at an appropriate site as per participant. For both adolescents and parents, we also gather self-reported data (noted in Table 2). These data will be captured via our secure mobile data collection device at the household (or by phone if this is not possible after 2 visits; during the COVID-19 crisis, we will utilize phone collection as the default modality of data collection), guided by trained study staff (e.g., assessment team). We anticipate assessments lasting 1-1.5 hours in home visits, and administered separately to caregiver/parent and adolescent to protect confidentiality. The PIs and/or Project Manager will also monitor assessments, rotating randomly with individual staff in the field (e.g., assessment team) and contactable by cell-phone to troubleshoot with other RAs. Data on initial intervention efficacy will be assessed at 3 time points: baseline, 6- and 12-months post-intervention. The countdown clock for the immediately 6- and 12-month assessments occur starting the first day after the last intervention session and we aim to collect these assessments within a 2-8 week window. During

the COVID-19 crisis, we will make two additional changes. First, regarding the time points, we will try to collect all non-biological data at the 6- and 12-month windows as planned, and then collect the biological HIV and STI outcomes when movement restrictions and/or contact precautions regarding COVID-19 transfer can be reasonably lifted. If this approach results in large amounts of missing data, we will then attempt to collect all data (biological and non-biological data) when movement restrictions and/or contact precautions regarding COVID-19 transfer can be reasonably lifted. Second, during the COVID-19 crisis, we will attempt to collect all data within a 2-8 week window, but will attempt to gather data outside of these countdown windows to limit missing data. In order to increase the reliability of measurements, for data on hypothesized effects, we choose measures informed by preliminary studies, mentor's research in South Africa, and original Family Talk and Keepin' It Real studies to be culturally and contextually appropriate. Measures have been translated previously in South Africa. We also increase reliability by focusing on measures with strong psychometric properties, and when possible with piloting and pre-testing in South Africa. In addition, we increase reliability by programming to decrease human error (e.g., logic scenarios for questions within a skip pattern). Furthermore, for sensitive questions, we administer questions via private earphones plugged into mobile data collection devices using *Audio Computer-Assisted Self-Interview Software* (A-CASI). This method has been shown to diminish social reporting bias. We will not be able to implement A-CASI if we move to remote telephone collection due to the COVID-19 crisis.

We investigate fidelity assessments (coding a minimum of 15% of sessions), we follow recommendations issued by the Treatment Fidelity Workgroup of the NIH Behavior Change Consortium to ensure coding of fidelity based on a standardized monitoring checklist to assess: 1) facilitator adherence/drift from fidelity. These fidelity assessment will be gathered in real time, as intervention facilitators deliver the intervention. We will also gather data to understand attrition which gives us information on another aspect of feasibility. This will include gathering characteristics on who is eligible (from baseline data) but does not attend the enrollment session; data on who fills out baseline, post-, and 3 month assessments; as well as who attends scheduled intervention sessions. We gather process data including data on treatment integrity by examining the rigor of the intervention implementation to the standardized manualized protocol through fidelity data. Fidelity coding will be conducted on 10-15% of total sessions using a neutral coder, ranking integrity and competency of session delivery in real time, and following recommendations issued by the Treatment Fidelity Workgroup of the NIH Behavior Change Consortium^157 We also track recruitment, retention, and attrition data using FileMaker Software to identify ways for optimization of the intervention in future dissemination, implementation, and scale-up should it show efficacy. This will include gathering characteristics on who is eligible (from baseline data) but do not attend the enrollment session as well as who attends scheduled intervention sessions. For process data we recruit adolescents, parents, and stakeholders including representatives from DTHF, a well-established community organization that is an ideal target for future scale-up and implementation research for in-depth interviews (N=30-45) with final sample size is based on data saturation. We anticipate these assessments will take 10 minutes. We also gather process data through qualitative in-depth interviews in Aim 3. All measures are provided for full review. There will be no additions to the questionnaire (see Appendix) without approval of the IRB, although some questions may be cut to reduce survey length after piloting.

**Retention.** We gather information to help track and retain participants including: 1) at baseline, documenting multiple participant contact details (address, phone numbers), names and phones of three individuals who know how to contact the family; 2) monthly contact via telephone or text with reminders for upcoming appointments and to update contact information; 3) geo-

location data to facilitate in-home assessments in a context where homes often do not have addresses or street names. We will also provide participants with reminder cards with study staff contact details and timeframes (and if possible, exact dates), and locations for follow-up data collection. We will attempt to contact participants who are not available at home, for participation in follow-up data collection to either meet them at their home or utilize the telephone to complete data collection.

